6.4.1.2 Primary Efficacy Variables

Phase 2 Adjuvant (Group 1):

- RFS: defined as the time between the date of randomization and the date of first relapse per ELN recommendations or death by any cause, whichever occurs first. Relapse includes either hematologic and/or molecular relapse as defined in [Table 2](#) at any disease assessment. In the event that no relapse or death is documented prior to analysis cutoff or the start of new anti-cancer therapy, RFS will be censored on the date of the last evaluable disease assessment demonstrating no relapse prior to analysis cutoff or the start of new therapy. For patients who remain alive and have no baseline disease assessment or have no post-randomization disease assessment, RFS will be censored on the date of randomization. In addition, if relapse or death occurs after extended time without disease assessments, RFS will be censored on the date of the last evaluable disease assessment prior to the missed disease assessments.

For patients with relapse or death, a variable will be created to flag whether the earlier date of relapse or death occurs after extended time without disease assessments. The extended time is defined as below:

- Time from randomization date to Day 0 visit + 12 weeks + assessment window of 2 weeks, if the latest assessment prior to the event (relapse or death, whichever is earlier) \leq randomization date + 0.5*time from randomization date to Day 0 visit. For patients without Day 0 visit, an artificial Day 0 visit will be derived as randomization date + mean time from randomization date to Day 0 visit date in MT-401 arm, for analysis purpose only.
- 24 weeks + assessment window of 2 weeks, if the latest assessment prior to the event (relapse or death, whichever is earlier) \leq Day 0 visit + 6 weeks & $>$ randomization date + 0.5*time from randomization date to Day 0 visit
- 38 weeks + assessment window of 5 weeks, if the latest assessment prior to the event (relapse or death, whichever is earlier) \leq Day 0 visit + 18 weeks & $>$ Day 0 visit + 6 weeks
- 78 weeks + assessment window of 5 weeks, if the latest assessment prior to the event (relapse or death, whichever is earlier) \leq Day 0 visit + 37 weeks & $>$ Day 0 visit + 18 weeks
- 104 weeks + assessment window of 5 weeks, if the latest assessment prior to the event (relapse or death, whichever is earlier) \leq Day 0 visit + 78 weeks & $>$ Day 0 visit + 37 weeks

Phase 2 Active Disease (Group 2):

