- CR: For Subgroup C, CR is defined as the proportion of patients who achieve a best response of CR_{MRD-} or CR using the ELN recommendations. For Subgroup D, CR rate is defined as the proportion of treated patients who achieve a best response of CR_{MRD-}. Best overall response (BOR) is defined as the best response designation recorded between the date of first dose and the date of objectively documented relapse per ELN recommendations or the date of subsequent therapy, whichever occurs first. For patients without documented relapse or subsequent therapy, all available response designations will contribute to the BOR assessment.
 - The incidence of converting MRD+ to MRD- was chosen as the primary endpoint for Subgroup D based on the following rational: (1) 2017 ELN recommendations (Döhner et al, 2017) introduced a new response category of CR MRD- recognizing MRD assessment provides a more reliable predictor of outcome than morphological assessment and MRD status has been consistently shown to be an independent prognostic marker for disease outcome (Short et al, 2020; Schuurhuis et al, 2018). (2) Given the nature of single arm design, a binary endpoint was considered a more appropriate primary endpoint than a time to event endpoint such as RFS or OS.
- DOCR: For Subgroup C, DOCR is defined as the time between the date of first documented response of CR_{MRD-} or CR to the date of the first documented relapse per ELN recommendations or death due to any cause, whichever occurs first. For Group 2 Subgroup D, duration of complete response is defined as the time between the date of first documented response of CR_{MRD-} to the date of the first documented relapse per ELN recommendations or death due to any cause, whichever occurs first. For patients who neither relapse nor die prior to analysis cutoff or the start of new anti-cancer therapy, DOCR will be censored on the date of their last evaluable disease assessment on or after the assessment of first documented CR and prior to analysis cutoff or start of new therapy.

6.4.1.3 *Secondary Efficacy Variables*

Safety Lead-in (Cohorts I and II) and Cohorts III-V:

- CR (Active disease patients): defined as above for Group 2
- DOCR (Active disease patients): defined as above for Group 2

Phase 2 Adjuvant (Group 1):

- OS: defined as the time between the date of randomization and the date of death. A patient who has not died will be censored on their last contact date (“last known alive date”).

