- Graft-versus-host disease RFS (GRFS): defined as the time from randomization to date of GVHD, relapse, or death, whichever occurs first. A GVHD event is defined as any grade

3-4 acute GVHD or chronic GVHD requiring systemic therapy. A patient who has not experienced any of these events prior to analysis cutoff or the start of new anti-cancer therapy, will be censored on the earlier date of their last GVHD assessment and evaluable disease assessment demonstrating no relapse prior to analysis cutoff or start of new therapy. For patients who remain alive and have no baseline disease assessment or have no recorded post-randomization disease assessment, GRFS will be censored on the date of randomization. In addition, if a GVHD event, relapse, or death occurs after extended time without GVHD assessments, GRFS will be censored on the date of the last evaluable GVHD assessment prior to the missed GVHD assessments or on the date of the last GVHD assessment prior to the missed GVHD assessments.

Phase 2 Active Disease (Group 2):

- ORR: defined as the proportion of treated patients who achieve a best response of CR_{MRD}-, CR, CRi, MLFS, or PR using the ELN recommendations and repeated MRD assessment. This endpoint only applies to Group 2 Subgroup C.
- DOR: defined as the time between the date of first documented response of CR_{MRD}-, CR, CRi, MLFS, or PR to the date of the first documented progression per ELN recommendations or death due to any cause, whichever occurs first. For patients who neither progress nor die prior to analysis cutoff or the start of new anti-cancer therapy, DOR will be censored on the date of their last evaluable disease assessment on or after the assessment of first documented CR_{MRD}-, CR, CRi, or PR and prior to analysis cutoff or start of new therapy. This endpoint only applies to Group 2 Subgroup C.
- PFS: defined as the time between the date of first dose and the date of documented progression or death by any cause, whichever occurs first. For patients who remain alive and whose disease has not progressed prior to analysis cutoff or the start of new anti-cancer therapy, PFS will be censored on the date of last evaluable disease assessment prior to analysis cutoff or start of new therapy. For patients who remain alive and have no baseline disease assessment or have no recorded post-dose disease assessment, PFS will be censored on the date of first dose of study medication. This endpoint only applies to Group 2 Subgroup C.

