Patients with no post-baseline disease assessment will be included in the denominator for calculation of CR and ORR and will be treated as non-responders.

For time to event endpoints (RFS, OS, GRFS, PFS), patients with no baseline disease assessment or no post-baseline disease assessment will be censored using a censored value of 1 day.

No other imputations of missing data will be made.

7.4.7.3 *Interim Analyses and Data Monitoring*

A Sponsor review committee (SRC) will be convened to review the toxicities and endpoints related to the Safety Lead-in (Cohorts I and II), meet separately once Cohort III is complete and again once Cohorts IV-V are complete. The SRC will consist of at least 1-2 clinicians that includes the Medical Monitor and/or the Medical Director, along with 1 statistician.

Safety data will be reviewed at the end of the Safety Lead-in to determine if it is appropriate to move forward with the specific peptide manufacturer in the Phase 2 portion of the study. The evaluation of DLTs will be conducted in the DLT-evaluable set. Safety data will also be reviewed at the end of Cohort III to determine if it is appropriate to switch to a higher dose in the Phase 2 portion of the study. Additionally, safety data will also be reviewed at the end of Cohorts IV and V to determine if it is appropriate to switch to a dosing regimen with the MT-401 product manufactured using the accelerated process in the Phase 2 portion of the study. This decision will be made by the Sponsor based on multiple parameters, including the safety and biomarker data available.

A DMC will be formed for the Phase 2 portion of the study. The DMC will make recommendations on ongoing study conduct, including the accrual of additional patients to Group 1 based on the futility and efficacy criteria outlined below and any additional criteria established in the DMC charter. In addition, an Independent Efficacy Review Committee (IERC) may be formed to provide independent disease assessment. Separate charters will outline the details, including roles and responsibilities of these two committees.

Two formal interim analyses are planned during Phase 2, one for Group 1 and one for Group 2.

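### SAP 7.4.7.2 censors RFS, OS, GRFS and PFS at day 1 with no condition that the patient is alive, contradicting the SAP's own definitions and the protocol; the expected effect on Group 1 RFS is small

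*SAP*

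**What the plan says.** SAP 7.4.7.2 (Handling of Dropouts or Missing Data) gives one rule for four endpoints: "For time to event endpoints (RFS, OS, GRFS, PFS), patients with no baseline disease assessment or no post-baseline disease assessment will be censored", with a value of 1 day. It adds that no other imputation will be made.

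The SAP definitions read differently:

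- **RFS (6.4.1.2).** Death by any cause is an event. "For patients who remain alive and have no baseline disease assessment or have no post-randomization disease assessment, RFS will be censored" at randomization. A separate rule covers long gaps: "if relapse or death occurs after extended time without disease assessments, RFS will be censored on the date of the last evaluable disease assessment". For a patient not assessed since about the time of randomization, the gap is "Time from randomization date to Day 0 visit + 12 weeks + assessment window of 2 weeks".
- **GRFS (6.4.1.3).** It is "defined as the time from randomization to date of GVHD, relapse, or death, whichever occurs first". "For patients who remain alive and have no baseline disease assessment or have no recorded post-randomization disease assessment, GRFS will be censored" at randomization.
- **PFS (6.4.1.3).** "For patients who remain alive and have no baseline disease assessment or have no recorded post-dose disease assessment, PFS will be censored" at first dose.
- **OS (6.4.1.3).** "A patient who has not died will be censored on their last contact date". Disease assessments play no part.

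The protocol text (9.3.2, 9.3.4.1, 9.3.4.2 and 9.3.4.4) agrees with the definitions. SAP section 4 promises to explain any change from the protocol, and SAP 7.7 declares none.

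**The concern.** Two rules in the same SAP treat the same patient differently. A patient who dies before any post-baseline disease assessment is an event under the definitions and a day-1 censoring under 7.4.7.2. No sentence says which governs. RFS is the primary endpoint of Group 1 and drives the 45-event interim analysis and the 90-event primary analysis. If 7.4.7.2 were programmed as written, early deaths would leave the RFS estimate, and the same deaths would leave OS, where they would otherwise still be visible. The SAP says it exists to avoid post hoc decisions. Here it would force one, about early deaths, in an unblinded trial.

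**Working it through.** **1. The texts side by side**

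| Endpoint | Definitions (SAP 6.4.1.2, 6.4.1.3; protocol 9.3) | SAP 7.4.7.2 | Difference |
|---|---|---|---|
| RFS | Unassessed and alive: censored at randomization. Death: event, unless after the extended gap | Unassessed, alive or dead: 1 day | Deaths inside the gap limit |
| GRFS | Same, with GVHD also an event and the gap rule based on GVHD assessments | 1 day | Deaths, and GVHD events, inside the limit |
| PFS | Unassessed and alive: censored at first dose. Death: event | 1 day | Unassessed deaths |
| OS | Death: event. Alive: censored at last contact | 1 day | Unassessed deaths, and all follow-up of unassessed living patients |

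The value of 1 day is not itself a conflict for RFS, GRFS and PFS. SAP 7.1.4 counts durations as later date minus earlier date plus 1, so censoring on the start date gives 1 day. For OS it is a conflict.

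RFS limit: with Day 0 falling 5 to 50 days after randomization, the first gap is 5 + 98 = 103 to 50 + 98 = 148 days. Later unassessed deaths are censored under the definition too.

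**2. The plan's own figure**

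Events for 80% power at HR 0.55, two-sided 0.05: 4(1.96 + 0.8416)²/(ln 0.55)² = 87.8, so 88. Power at 90 events: Φ(0.598 × √90/2 − 1.96) = 0.809. The stated 90 events and 80% reproduce, and this point does not dispute them.

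**3. How many Group 1 patients die before a first assessment**

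From the documents: 75 per arm; median RFS 8 and 14.5 months; Day 0 at days 85-130 post-HSCT; the Day 0 assessment may be omitted within 3 weeks of the prior one; otherwise the next is Week 12 ± 1. Assumed: exponential RFS; Day 0 uniform over its range; a share d = 10-30% of first RFS events are deaths; the Day 0 assessment is skipped by everyone allowed to, or by nobody.

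Expected deaths per arm = 75 × d × mean of [1 − exp(−λT)], with λ = ln 2/8 or ln 2/14.5 per month and T the time from randomization to the first assessment.

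Randomized at day 80 (skipping possible up to day 80 + 21 = 101):

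- With skipping: 11.05 (SoC) + 6.38 (MT-401) = 17.43 first events; × 0.1 to 0.3 = 1.7 to 5.2 deaths.
- Without skipping: 5.60 + 3.15 = 8.75; × 0.1 to 0.3 = 0.9 to 2.6 deaths.

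Overall 0.9-5.2 of 150. The same calculation gives 0.6-4.0 at day 90 and 0.5-1.7 at day 100. Day 80 is the upper end, because central MRD results must precede randomization. Unscheduled and discontinuation visits, which follow the Week 24 assessments, lower these counts.

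**4. At the analyses**

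With 150 patients accrued uniformly over 50 months, expected events per arm by month t are 1.5 × [t − (1 − e^(−λt))/λ]. The two arms sum to 90 at t ≈ 44.9 and to 45 at t ≈ 28.0. At 3 patients per month, about 135 and 84 are then randomized. The day-80 range becomes 0.9-5.2 × 135/150 = 0.8-4.7 at the 90th event and × 84/150 = 0.5-2.9 at the 45th.

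**5. Effect on RFS under the planning assumptions**

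Simulation: randomized at day 80 with skipping, cut at 90 events, Cox Wald test, 3,000 trials per row, death shares 10/20/30%.

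| | Definition | 7.4.7.2 literal |
|---|---|---|
| Mean HR (true 0.55) | 0.561/0.564/0.563 | 0.561/0.563/0.562 |
| Power | 78.8/78.7/78.6% | 78.9/79.2/79.0% |
| False positive favouring MT-401 (true HR 1) | 2.7/2.6/2.4% | 2.8/2.7/2.5% |
| Month of 90th event | 44.7 | 45.3/45.8/46.4 |

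**6. If the deaths cluster**

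Illustration only: two extra unassessed deaths, uniform over the first 1.6 months, 4,000 trials. Each cell runs from definition to literal rule.

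| Placement | Mean HR (true 0.55) | Power | P(HR > 1.1) at 45 events, true HR 1 |
|---|---|---|---|
| Both MT-401 | 0.592 to 0.563 | 72.2% to 78.9% | 42.4% to 37.6% |
| Both SoC | 0.547 to 0.562 | 82.3% to 79.0% | 32.8% to 37.8% |
| One each | 0.573 to 0.566 | 76.8% to 78.4% | 38.1% to 37.8% |

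**7. OS**

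The documents give no survival figure for Group 2, so the counts here are assumed. In Subgroup C (n = 30), 1, 3 or 6 deaths before any post-baseline assessment give Kaplan-Meier OS of 29/30 = 96.7%, 27/30 = 90.0% or 24/30 = 80.0% under the definition. With no other deaths, the literal rule gives 100% each time.

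**The case against.** The best reply is that the intent is clear. SAP section 4 says changes from the protocol will be explained, SAP 7.7 declares none, and the protocol limits the censoring to living patients. The RFS gap algorithm in 6.4.1.2 has a case for patients last assessed around randomization and even derives an artificial Day 0 for those without one. That would have little purpose if every unassessed death were censored at day 1. With the plus-1 convention, 7.4.7.2 can be read as shorthand for the existing rule for RFS, GRFS and PFS. This stands, and it makes literal programming of the primary endpoint less likely. It does not rescue OS, where even a living patient would be censored at day 1 rather than at last contact. Nor does it replace a statement of which text governs.

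A reader might also infer that GRFS has a settled second error: that a living patient with qualifying GVHD and no disease assessment is censored at randomization. The documents do not go that far. Protocol Table 11 counts GVHD as an event, and in the SAP the sentence follows one about patients with none of the events. It is an ambiguity. Nor does the schedule, with GVHD visits at Weeks 2 and 4 that SoC patients may omit, make it a general bias between arms. The rule touches only a patient never assessed for disease after randomization.

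**Conclusion.** The contradiction is textual and holds for all four endpoints. For OS the rule in 7.4.7.2 is wrong as written. For RFS, GRFS and PFS it is wrong if followed literally, and for RFS only for deaths within randomization-to-Day-0 plus 14 weeks.

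The expected effect on Group 1 RFS is small: 0.9-5.2 of 150 patients at day 80, fewer at the two analyses, a 90th event 0.6-1.7 months later, and essentially unchanged HR, power and type I error. This rests on exponential RFS and an assumed 10-30% share of deaths among first events.

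A reader might infer that the primary analysis is biased toward MT-401. The documents do not support that. They give no early-death rate by arm, so the direction is unknown; the larger shifts appear only when extra deaths are placed in one arm, and they favour whichever arm has them. The interim futility rule is non-binding, Group 1 OS and GRFS are descriptive, and the Group 2 primary endpoints (CR rate, DOCR) are not in the sentence. This should be fixed, but it does not show that the primary analysis is compromised.

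**What to change.** In SAP 7.4.7.2:

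- Delete OS, and state that OS is censored only at the last known alive date.
- For RFS and PFS, restrict the rule to *patients who are alive with no baseline or no post-baseline disease assessment*.
- For GRFS, restrict it to such patients who are also *without a qualifying GVHD event*, and add the same words to the GRFS definition in 6.4.1.3.
- State that deaths are events on the date of death, subject to the existing new-therapy and extended-gap rules.

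The rows of protocol Tables 9, 11 and 12 for patients without a baseline assessment also omit the no-death condition. Record in SAP 7.7 that they are read with it, and align the tables at the next amendment. Few if any Group 1 patients should fall there, since a central MRD result is needed before randomization.

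Optional and minor: in the RFS gap rule the nominal gaps of 38 and 78 weeks should be 40 (52 − 12) and 80 (104 − 24). With their windows, the stated totals of 43 and 83 weeks already exceed these, so this affects about one RFS event or fewer.

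The cost is a few SAP sentences and some programming constants, with no new data. It is best done before the SAP is finalized for the interim analysis. Only the protocol tables need IRB/IEC approval, and they can wait.

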4.3.2. Main Portion of the Phase 2 Study

Following completion of the Safety Lead-in portion the study will proceed to open Groups 1 and/or 2 of the Phase 2 study at the highest cleared dose of 100×10^6 cells (DL4 – 50×10^6 cells/m²) from the Phase 1 trial. Briefly, in the dose escalation portion of the Phase 1 ADSPAM study, 50 x 10⁶ cells/m² cohort (DL4 - 100 x 106 cells) completed evaluation with 2 patients, and neither patient had any DLTs noted. A 100 x 10⁶ cells/m² dose cohort (DL5 – 200 x 10⁶ cells) has completed the DLT period for 1 patient without any DLTs noted. Therefore, patients in Groups 1 and 2 will receive three consecutive flat doses of 100 x 10⁶ cells every 2 weeks. MT-401 will be given by IV infusion through either a peripheral or central line. The patients will be monitored for any safety concerns for 1 hour after infusion as outpatients.

In total, approximately 210 patients will be treated in the Phase 2 portion of the study. The Phase 2 portion includes two groups of patients who will be treated with product as adjuvant therapy (Group 1) or

Confidential Page 31 of 74

with active disease (Group 2). Approximately 150 patients will be randomized 1:1 to either MT-401 product or standard of care therapy in Group 1 (adjuvant) and 60 patients with active disease will be treated in Group 2.

Following completion of Cohorts I and II, the confirmed peptide manufacturer to be used in Phase 2 will be identified based on review of the safety data. At any time, following completion of Cohort III the Sponsor may change the Phase 2 dosing regimen to that evaluated in Cohort III. At the conclusion of Cohorts IV and V, which evaluate the safety of the product manufactured using an accelerated process at two different doses, the Sponsor may change the Phase 2 dose to the dose deemed to be safe for MT-401 manufactured using the accelerated process.

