9. STATISTICAL CONSIDERATIONS

9.1. Sample Size Determination

9.1.1. Adjuvant Population (Group 1)

A total of approximately 150 Group 1 patients will be randomized with a 1:1 allocation to receive MT-401 or to be under observation (SoC arm). Median RFS for the SoC arm is expected to be approximately 8 months (Rashidi et al, 2016; Goyal, 2016). A clinically meaningful increase in median RFS for the MT-401 arm over SoC is thought to be 2 months or more. The primary analysis will be conducted when 90 RFS events have been observed. Ninety (90) RFS events provides 80% power with alpha=0.05 to detect a median RFS improvement of 6.5 months over the assumed SoC median RFS of 8 months (hazard ratio=0.55). Ninety RFS will be observed assuming uniform accrual of 150 patients (75 per arm) over a 50-month period and an additional 12-month minimum follow-up period. The DMC and Sponsor will review data from Phase 2 based on the planned interim analyses described in Section 9.5.

If the decision is made to dose patients in Phase 2 with any of the MT-401 dosing regimens evaluated in Cohorts III-V, enrollment will continue in Phase 2 Group 1 to achieve 150 evaluable patients randomized and approximately 75 patients treated with the final MT-401 dose and the intended manufacturing process, thereby replacing any patients that have not been treated with the final Phase 2 product, as determined by the Sponsor.

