7.2 Analysis Populations

The analysis populations are defined as follows:

- All Treated Patients: Includes all patients who received at least one dose of MT-401 or were randomized to SOC.
- All Randomized Patients: Includes all patients in Group 1 who were randomized with final dose and manufacturing process and are MRD⁻ prior to randomization by central testing and local testing, if a local test was also performed. A patient randomized based on negative MRD result per central test but confirmed to be MRD⁺ will be excluded from Group 1 analysis.

When MRD testing occurs with different methodology (eg, flow cytometry and PCR), the patient is considered MRD⁺ if either test detects MRD. If adjudication occurs between central testing and local testing for the same type of testing (eg, flow by central testing and flow by local testing), the final adjudicated result will be taken into account for the confirmed MRD result. A patient confirmed to be MRD⁺ prior to randomization will be excluded from Group 1 and will be included in Group 2 analysis if treated with MT-401.

- Per-Protocol (PP) Population: Includes all treated patients, as defined above, who have no major protocol deviations. If there is <5% difference in the all randomized patient population and the PP population for Group 1, no analyses will be performed on the PP population.

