The interim analysis for Group 1 will occur when 45 RFS events have occurred. It is anticipated that this will occur approximately 30 months after the first patient randomized. At this analysis, the DMC will assess safety, futility, and potential expansion of study accrual. At the time of this analysis, enrollment of the remaining patients will continue, unless any safety concerns are identified.

The following options for the Group 1 interim analysis will be considered:

- Option 1: Terminate Group 1 due to futility if the RFS hazard ratio for MT-401:SOC is larger than 1.1 at the interim analysis. This futility stopping rule will be non-binding and can be overridden by the DMC and/or Marker.
- Option 2: Retain the planned target number for patient accrual and planned 90 RFS events if the conditional power (CP) calculated at the interim analysis is greater than 80% or less than 50% and the futility stopping rule is not met.
- Option 3: Increase the target number of planned accrual and RFS events if CP is between 50% and 80% and the futility stopping rule is not met. The target number of RFS events will be increased to achieve CP of 80% or increase by 50%, whichever is smaller. Target enrollment adjustments will be accomplished based on pooled event accumulation rate and a reasonable study duration projected via simulation.

The interim analysis for Group 2 will occur after the first approximately 10 patients in each subgroup have progressed or had the opportunity to be followed for 6 months. Clinical safety and efficacy will be reviewed comprehensively. Further enrollment for a subgroup may be terminated due to futility based on totality of the data. Patients treated in Cohorts IV-V with the same

manufacturing process as Group 2 may be included in Group 2 Subgroup C or Subgroup D analyses for decision making.

7.4.7.4 *Multicenter Studies*

This is a multicenter study, with approximately 20-25 study centers expected to participate. Efficacy data collected from all study centers will be pooled for data analysis. The effect of study center on the efficacy analysis results may be explored post-hoc, as needed.

7.4.7.5 *Multiple Comparisons/Multiplicity*

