7.6 Determination of Sample Size

Approximately 6-12 patients are expected to be enrolled in the Safety Lead-in portion of this study per a standard 3+3 design with 2 planned cohorts. In addition, approximately 9-18 patients (3-6 patients per cohort) are expected to be treated in the Cohorts III-V portion of this study as per a standard 3+3 design.

A total of 150 Group 1 patients will be randomized with a 1:1 allocation to receive MT-401 or to be under observation (SOC arm). Median RFS for the SOC arm is expected to be approximately 8 months. A clinically meaningful increase in median RFS for the MT-401 arm over SOC is thought to be 2 months or more. The primary analysis will be conducted when 90 RFS events have been observed. Ninety (90) RFS events provides 80% power with alpha=0.05 (two-sided) to detect a median RFS improvement of 6.5 months over the assumed SOC median RFS of 8 months (hazard ratio=0.55). Ninety RFS will be observed assuming uniform accrual of 150 patients (75 per arm) over a 50-month period and an additional 12 month minimum follow-up period. The DMC and Sponsor will review data from Phase 2 based on the planned interim analyses described in [Section 7.4.7.3](#).

If the decision is made to dose patients in Phase 2 with any of the MT-401 dosing regimens evaluated in Cohorts III-V, enrollment will continue in Phase 2 Group 1 to achieve 150 evaluable patients randomized and approximately 75 patients treated with the final MT-401 dose and the intended manufacturing process, thereby replacing any patients that have not been treated with the final Phase 2 product, as determined by the Sponsor.

A total of approximately 60 Group 2 patients are planned to be enrolled and treated with MT-401, 30 patients in Subgroup C (frank relapse patients) and 30 patients in Subgroup D (MRD⁺). After approximately 10 patients in each subgroup have progressed or had the opportunity to be followed for 6 months, clinical safety and efficacy will be reviewed comprehensively. Patients who develop CR_{MRD-} after bridging therapy and patients who relapse early (defined as less than 90 days ± 10 days and termed Group 2 Early Relapse patients) will be analyzed separately, and not be counted as part of the 60 patients in Group 2.

The sample size of 30 per subgroup is not based on a formal power calculation. An increase in the CR rate of greater than 10-15% compared to historical rates for standard of care would be considered clinically meaningful.

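### Group 1 RFS: the documents conflict on whether the Sponsor sees the 45-event interim, and nothing requires the product that defines the analysis set to be fixed before it, or without knowledge of it

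*SAP*

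**What the plan says.** **Who reviews the interim.** Protocol 9.1.1, in the Group 1 sample-size paragraph, says "The DMC and Sponsor will review data from Phase 2 based on the planned interim analyses described in Section 9.5". SAP 7.6 repeats this: "The DMC and Sponsor will review data from Phase 2 based on the planned interim analyses". Protocol 4.1 and 9.5.1 and SAP 6.1 and 7.4.7.3 assign the 45-event Group 1 look to the DMC. Protocol 4.1 and SAP 6.1 then describe the Sponsor's own review as a review of Group 2. On the futility rule (HR above 1.1), SAP 7.4.7.3 adds: "This futility stopping rule will be non-binding and can be overridden by the DMC and/or Marker".

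**Who fixes the product, and when.** Protocol 4.3.2 states: "At any time, following completion of Cohort III the Sponsor may change the Phase 2 dosing regimen to that evaluated in Cohort III". It allows a move to the accelerated product once Cohorts IV and V conclude. Protocol 9.5 and SAP 7.4.7.3 leave this decision to the Sponsor on several parameters, with safety and biomarker data given as included examples.

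**Who is analysed.** SAP 7.2 defines the Group 1 efficacy set: "Includes all patients in Group 1 who were randomized with final dose and manufacturing process". Protocol 9.2 (Table 8) agrees. Protocol 9.1.1 and SAP 7.6 replace patients not treated with the final product, as the Sponsor determines.

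**What is claimed.** SAP 7.4.7.5 tests RFS at two-sided 0.05 at the final analysis. It relies on a cited method for increasing sample size after a promising interim to hold that level.

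**The concern.** A type I error statement holds when the set of patients tested does not depend on the comparison being tested. Here the set is defined by a product decision that the Sponsor makes, that may fall after the interim, and whose stated inputs do not exclude Group 1 RFS. Two passages name the Sponsor as a reviewer of the planned interims. If the decision were taken knowing a disappointing hazard ratio, the patients behind that result would leave the primary analysis and a new test would be run at full alpha. Group 1 RFS is the trial's only randomized primary comparison, so its error rate should be secured by the text.

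**Working it through.** **1. The plan's own figure.** SAP 7.6: "Ninety (90) RFS events provides 80% power with alpha=0.05 (two-sided) to detect a median RFS improvement of 6.5 months", with hazard ratio 0.55 and 1:1 allocation. By Schoenfeld, power = Φ(√90/2 × |ln 0.55| − 1.96) = Φ(4.743 × 0.598 − 1.96) = Φ(0.876) = 0.809. With HR = 8/14.5 = 0.552, power is 0.805. The stated 80% is reproduced.

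**2. Is the order of events fixed?** Cohorts III-V run in parallel with Phase 2 (protocol 4.1). The interim is expected about 30 months after the first randomization (SAP 7.4.7.3), within a 50-month accrual (SAP 7.6). The product may change at any point after Cohort III, or after Cohorts IV and V. No section orders the decision relative to the 45-event look, and none restricts who may know Group 1 RFS by arm when it is made.

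**3. Model for a results-driven switch.** Take HR = 1. Let Z1 be the log-rank statistic at 45 events and Zf the statistic at 90, both positive in favour of MT-401, with correlation √(45/90) = 0.707. An interim hazard ratio h corresponds to c = −ln(h) × √45/2 = −ln(h) × 3.354. Suppose the product is switched when the interim HR exceeds h (Z1 < c), earlier patients in both arms are dropped, and 90 wholly new events are tested at 1.96. Then:

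- favourable-direction error = P(Z1 ≥ c, Zf > 1.96) + P(Z1 < c) × 0.025
- two-sided error = P(Z1 ≥ c, |Zf| > 1.96) + P(Z1 < c) × 0.05

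For h = 1.1, c = −0.320 and P(Z1 < c) = 0.3746. Favourable: 0.0249 + 0.3746 × 0.025 = 0.0343. Two-sided: 0.0258 + 0.3746 × 0.05 = 0.0445.

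| Switch if interim HR exceeds | P(switch) under HR = 1 | Favourable (nominal 0.025) | Two-sided (nominal 0.05) |
|---|---|---|---|
| 1.1 | 0.375 | 0.0343 | 0.0445 |
| 1.0 | 0.500 | 0.0372 | 0.0500 |
| 0.9 | 0.638 | 0.0400 | 0.0560 |
| 0.8 | 0.773 | 0.0415 | 0.0609 |
| about 0.79 (favourable maximum) | 0.792 | 0.0416 | not shown |
| about 0.71 (two-sided maximum) | 0.870 | not shown | 0.0625 |

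At h = 1.1 the two-sided total is below 0.05 because interim results in the harmful direction are discarded. The chance of a false claim of benefit still rises by a factor of 0.0343/0.025 = 1.37.

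**4. Other features, checked separately.**

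- Futility override: favourable-direction error is 0.0250 if the rule is never applied and 0.0249 if always applied.
- Event increase, up to 50% more events (135), with the ordinary final test: 0.0245 if conditional power uses the interim trend, about 0.0256 if it uses HR 0.55. The SAP does not say which. This is what the method cited in SAP 7.4.7.5 is used for; it does not cover discarding first-stage patients and restarting.
- Switch independent of Group 1 RFS: 0.025 favourable, 0.05 two-sided.

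**The case against.** The best counter-argument is that the plan, read as a whole, already separates the roles. The sentence naming the Sponsor covers Phase 2 interims in the plural and points to protocol 9.5 and SAP 7.4.7.3, where the Group 1 look belongs to the DMC. Protocol 9.4 calls the DMC independent and defers to a charter, which may contain a firewall and is not among the documents. Product decisions are tied to end-of-cohort reviews of 3 to 6 patients with a 28-day DLT window, so they may well come before an interim expected at about 30 months. Because Group 1 efficacy is analysed only in patients on the final product, an interim in that set presupposes a settled product. A restart would also be expensive: on the plan's own assumptions, about 150 more patients over 50 plus 12 months. Finally, in the scenario closest to a futility override (HR>1.1), the two-sided total is under 0.05.

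Much of this stands. It makes a results-driven switch less likely and makes Sponsor access a contradiction to reconcile, not an established fact. It does not close the route. The population rule does not stop the final product from being redefined after the interim. The list of decision inputs is open. The two-sided total at HR>1.1 is low only because harmful interims are dropped.

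A reader might go further and infer three things that the documents do not support:

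- That the non-binding futility rule itself inflates alpha. It does not, since the final test takes no credit for stopping.
- That the Sponsor certainly sees the Group 1 comparison by arm. A right to override does not establish that, and four sections point the other way.
- That the product may change without restriction. The change must follow Cohort III, or Cohorts IV and V for the accelerated product.

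**Conclusion.** The point holds in a conditional form. The text does not assure the 0.05 stated in SAP 7.4.7.5, because a Sponsor-determined product defines the primary RFS set and nothing requires that determination to precede the 45-event interim or be made without knowledge of it. If one switch at that look depended on the hazard ratio, favourable-direction error would be 0.034 (HR>1.1) to at most 0.042 against 0.025, and the two-sided total 0.0445 to at most 0.0625 against 0.05. The largest values need a switch even when the interim moderately favours MT-401. A switch made without sight of Group 1 RFS leaves the error at 0.025 and 0.05, so it would be wrong to say that the level is already lost.

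The figures assume a single switch, both arms restarted, no overlap with earlier patients, and a normal approximation to the log-rank test. The Sponsor-access passages need reconciling in any case.

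**What to change.** 1. In protocol 9.1.1 and SAP 7.6 and 7.4.7.3, state that only the DMC sees Group 1 interim results by arm and that the Sponsor receives only the recommendation (stop, continue, or new event target). Bring protocol 4.1 and 9.5.1 and SAP 6.1 into line.
2. In SAP 7.2 and 7.4.7.3, state that the product defining the Group 1 analysis set is fixed and documented before the 45-event unblinding, or by people without access to Group 1 results by arm. Otherwise, patients randomized before the change stay in the primary RFS test. Item 1 alone is not enough: a recommendation to stop under the futility rule tells the Sponsor that the hazard ratio exceeded 1.1.

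It would help to say in the same edit whether SoC patients randomized before a switch remain in the analysis, and on which effect conditional power is computed.

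None of this bears on which dose or process is chosen. The cost is wording and a DMC firewall: the Sponsor gives up access to the interim comparison and some late flexibility. If the product does change late, the primary test may mix products.
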